Thus, good evidence suggests that at least acute treatment with ARBs could ameliorate lung injury in COVID-19. We therefore propose to test losartan in a Phase I proof of concept and safety trial. The primary hypothesis to be tested is that losartan treatment is safe in the setting of acute SARS-CoV-2 infection. Secondarily, losartan can potentially reduce the length of respiratory failure due to SARS-CoV-2.

Significance

Importance of the problem: As outlined above, there is currently no data that supports specific treatment options for respiratory failure in COVID-19. There are active or soon to be active clinical trials that may show promise in this space such as blocking IL-6 with tocilizumab²⁰ or using hydroxychloroquine. None of these therapies are without side effects and alternative or additional approaches could lessen the burden of respiratory failure in this patient population.

Approach and Protocol

This is an open label, phase 1 clinical trial to evaluate the safety of losartan in respiratory failure due to COVID-19.

Clinical Trial setup:

Detailed inclusion and exclusion criteria are listed below. Briefly, 50 patients with COVID-19 and respiratory failure who meet criteria and agree to participation in the study will be placed on losartan 25 mg daily on study day 0. If parameters are met the dose of losartan will be increased to 50 mg on study day 3. Participants will continue losartan until they experience resolution of respiratory failure (normal oxygen levels on room air), are discharged from the hospital, meet stoppage criteria (detailed below) or complete 14 days of therapy.

Primary hypothesis and endpoint:

- Losartan is safe in acute respiratory failure due to SARS-CoV-2.

Secondary endpoints:

- Losartan reduces the number of days on supplemental oxygen in respiratory failure due to COVID-19
- Incidence of mechanical ventilation use
- Days on mechanical ventilation
- Incidence of non-invasive positive pressure ventilation or heated high flow nasal cannula use
- Days on non-invasive positive pressure ventilation or high flow nasal cannula
- Incidence of transfer to ICU from non-ICU hospital bed
- ICU length of stay (days)
- In-hospital mortality
- Hospital length of stay (days)
- Cumulative incidence of severe adverse events
- Cumulative incidence of adverse events
- Change from baseline in oxygenation

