Patients that request to not be treated with Losartan will be approached by the study team to request permission for their standard of care treatment and data be followed and recorded by the research team for this study. Patients that agree, will sign the consent form, but will not provide a blood sample for research. We will also collect medical information relating to safety criteria on historical controls treated at the University of Kansas Hospital in the 30 days prior to the study start date (3/25/2020) and during the study period. These controls will be retrospectively identified through query of the electronic health record. We will attempt to include controls that meet all criteria for enrollment into the study but to achieve a ratio of controls to study participants of 2:1 may need include some with exclusion criteria (excluding prior ACE inhibitor or ARB use). Controls identified retrospectively will not undergo informed consent as this represents minimal risk.

Losartan

Losartan is an FDA-approved ARB widely prescribed for treatment of hypertension, heart failure, and for renal protection in patients with diabetes. The doses proposed in this study are well tolerated by non-hypertensive patients without significant effect on blood pressure. The proposed starting dose of losartan is 25 mg orally per day with increase to 50 mg orally per day on day 3 if tolerated until they patient is discharged from the hospital, met stoppage criteria (above) or completed 14 days of therapy.

The most common side effects are fatigue and dizziness. Serious adverse events that are rare include angioedema, hypotension, renal dysfunction or failure, blood dyscrasias, hepatitis, or rhabdomyolysis. The following are meant to mitigate risk to the subjects: Dosing will be done in an inpatient setting with clinically indicated close observations of blood pressure and organ dysfunction (blood work). Subjects with hyperkalemia, renal dysfunction, or who are taking potassium supplements will not be enrolled into the study. Participants will be given written descriptions of potential side effects and potential responses to the side effects.

Sample size and Statistics

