Since there is no information on the effects of losartan in human beings suffering from COVID-19, a statistical analysis based on efficacy is not possible. From a safety perspective, we would accept considering losartan equivalent or superior to the comparison group not receiving losartan (historical or no consent) if there is a $\pm 20\%$ difference in total AE/SAEs. Historical controls will be matched with study participants based on upon age, sex and disease severity in a 2:1 ratio for safety comparison. From a safety perspective, losartan's long track record as a safe medication is reassuring. See section on DSMB for further details on safety monitoring and analysis.

Confidentiality

All information provided by the subject to the investigators, and all information that is collected about the subjects by the investigators, shall be kept confidential to the extent that is provided by law. Computer data files will be stored and backup up to secure, HIPPA compliant, password protected computers and servers. Electronic data capture into REDCap system will be used. Access to these databases will be restricted to individuals associated with the study who require access to the data to perform their duties. These individuals will be named by the principal investigator prior to initiation of the clinical trial. The subject's actual identity cannot be ascertained exclusively from these data and the subject's name shall not be used in any publications. All investigators and staff involved in the research protocol will be bound by this agreement of confidentiality.

Adverse Event and Serious Adverse Event Documentation

Definition of an Adverse Event

For the purpose of this protocol, an AE will be defined as any untoward medical occurrence in a subject during the study listed under DMSB - Anticipated Adverse Events and Grading Scale section of this protocol as well as safety monitoring data listed on table 1 as well as stoppage criteria for losartan.

The event does not necessarily have a causal relationship with the treatment. AEs will be collected for both study groups, treatment and control from the time the ICF is signed until the subject completes study participation.

Definition of a Serious Adverse Event

An SAE is any AE that meets any of the following outcomes:

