 - Any serious AE or SAE attributable to study drug will be shared with the medical monitor and safety and monitoring group within 24 hrs. The members will make the decision whether or not to stop the trial.
- All SAEs will be reported to the safety and monitoring group and the appropriate agencies including FDA and IRB as required.
- All adverse effects will be reported according to the rules to the FDA, the IRB and our internal DMSB
- Initial interim analysis on safety will be done after the first 5 patients and reviewed by the internal DSMB.
- The DSMB may stop the study due to safety or futility.
- All DSMB reports will be shared with the IRB.

Safety Reporting

Data monitoring plans will be implemented as follows: The study will be closely monitored by the PI and Co-PIs. Any relevant AE or SAE will be reported to the medical monitor and to the DSMB (separate charter).

- DSMB meeting will occur after the first 5 patients, 25 patients and at end of study, or more frequently if needed.
 - Safety monitoring will be done by the DSMB. Safety monitoring will be done as follows: The investigators will continuously monitor the study for side effects. If any AE or serious adverse events (SAEs) occur, the physicians will assess the event and report them to the appropriate authorities if needed as per Good Clinical Practice. Subjects might be withdrawn from the study if they experience intolerance to the study medication, initially based on the investigators' discretion.
 - All adverse effects will be discussed among the investigators
 - If deemed severe the data will be shared with the medical monitor and the safety and monitoring group. The group will make the decision whether or not to stop the trial based on safety data.
- All SAEs will be reported to the IRB and the appropriate agencies including FDA as required.

- All adverse effects will be reported according to the rules to the FDA (if needed), the IRB and the DSMB.

Safety Reviews

Safety review will occur at least every month and/or if a SAE occurs. The internal safety and monitoring group will meet after the first 5 patients, 25 patients and at end of study or more frequently if needed. If needed, the biostatics core will assist in data analysis for adverse events as well (fee for service basis). However, this is a small study.

Removal of Subjects from Study

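### The safety rule compares AE/SAE totals from prospectively monitored losartan patients with totals from retrospectively identified controls, who have no defined AE window and cannot have every listed AE captured equally

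*Combined protocol and SAP*

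**What the plan says.** All references are to the combined protocol and SAP.

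- **Hypothesis and design.** The primary hypothesis is "Losartan is safe in acute respiratory failure due to SARS-CoV-2". The Approach and Protocol section describes the design: "This is an open label, phase 1 clinical trial to evaluate the safety of losartan in respiratory failure due to COVID-19". The treated number is given under Clinical Trial setup: "50 patients with COVID-19 and respiratory failure who meet criteria and agree to participation in the study will be placed on losartan".
- **Decision rule.** Under Sample size and Statistics, "we would accept considering losartan equivalent or superior to the comparison group not receiving losartan (historical or no consent") if total AE/SAEs differ by no more than ±20%. The section does not say whether this is relative or in percentage points, or whether events or patients are counted. Historical controls are matched 2:1 on age, sex and disease severity.
- **Losartan patients.** Study procedures require safety and stoppage monitoring on Days 1-2 and from Day 4 to completion. Safety Reporting adds: "The investigators will continuously monitor the study for side effects". The Losartan section gives participants written side-effect information.
- **Historical controls.** The Control section says: "These controls will be retrospectively identified through query of the electronic health record". It adds: "Controls identified retrospectively will not undergo informed consent as this represents minimal risk". Information on safety criteria is collected for them, and no patient contact is described.
- **AE window.** Definition of an Adverse Event: "AEs will be collected for both study groups, treatment and control from the time the ICF is signed until the subject completes study participation".
- **What counts as an AE.** The same section counts the anticipated-AE list, the Table 1 safety data and the losartan stoppage criteria. The first covers fatigue, dizziness, rash, palpitations and muscle pain. The last includes laboratory changes that the investigator judges potentially related to study drug.

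**The concern.** A difference in AE totals measures safety only if events are looked for in the same way, over the same period, in both groups. Here one group is observed at the bedside by investigators who know the treatment. The chart is the only implied source for the other.

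Some listed events depend on someone asking or writing something down. One of them, a laboratory change attributed to study drug, cannot occur in an untreated patient. Retrospective controls also have no start to the AE window, and no end in the sense of completing study participation.

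The primary conclusion is at stake. A difference in recording alone could use up some or all of the 20% allowance, or offset a real difference.

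**Working it through.** **The plan's own figures.** The plan gives 50 treated, a 2:1 ratio (2 × 50 = 100 controls) and a 20% margin. It states no AE rate, alpha, power or formula, so there is no calculation of its own to reproduce.

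**Passages side by side**

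| Element | Losartan patients | Historical controls |
|---|---|---|
| Source of AEs | Prospective monitoring plus the record | Record only, by implication |
| Window opens | Consent signature | Not defined: no consent form |
| Symptoms | Monitored; patients told what to look for | Only if charted |
| Laboratory change attributed to study drug | Can occur | Cannot occur |
| Laboratory grades in Table 1 | In the record | In the record, depending on draws |

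The mismatch in the window and in the attributed event needs no numerical assumption.

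**Size of effect.** Let p be the true patient-level AE risk, equal in both groups, and s the share of control AEs captured relative to losartan patients. Both are assumptions. Then:

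- observed ratio = p / (p·s) = 1/s
- observed difference = p − p·s = p(1 − s)

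Break-even points, with no true difference:

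- Relative reading: 1/s = 1.20 gives s = 1/1.2 = 0.833, whatever p is.
- Percentage-point reading: p(1 − s) = 0.20 gives s = 1 − 0.20/p. This is 0.33, 0.50, 0.60 and 0.71 for p = 0.3, 0.4, 0.5 and 0.7.

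Probability that the observed result meets the rule, from exact sums over two independent binomials (50 patients at p, 100 at p·s). PP means an absolute difference of at most 0.20 in either direction. Ratio means losartan rate at most 1.20 times the control rate.

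| p | Reading | s = 1 | s = 0.90 | s = 0.75 | s = 0.50 |
|---|---|---|---|---|---|
| 0.3 | PP | 0.990 | 0.985 | 0.953 | 0.772 |
| 0.4 | PP | 0.985 | 0.973 | 0.896 | 0.526 |
| 0.5 | PP | 0.982 | 0.962 | 0.824 | 0.293 |
| 0.7 | PP | 0.990 | 0.954 | 0.640 | 0.038 |
| 0.3 | Ratio | 0.768 | 0.623 | 0.368 | 0.063 |
| 0.4 | Ratio | 0.816 | 0.647 | 0.334 | 0.030 |
| 0.5 | Ratio | 0.864 | 0.674 | 0.300 | 0.012 |
| 0.7 | Ratio | 0.954 | 0.746 | 0.220 | 0.001 |

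If total AE/SAEs means event counts (Poisson, mean 1, 2 or 3 per patient), the ratio rule is met 86%, 94% and 97% of the time at s = 1, and 42%, 38% and 35% at s = 0.80.

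**How low could s be?** Suppose a share f of listed events in losartan patients are symptoms or attributed events, captured in controls at rate c, and all other events are captured fully. On the count scale s = 1 − f(1 − c). With c = 0.5, s falls below 0.833 once f exceeds (1 − 0.833)/0.5 = 0.33. For s to reach 0.50, f must be at least one half even if c = 0. The documents give neither f nor c.

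**The case against.** The strongest reply is that the AE list is closed and Table 1 dominates it: blood counts, creatinine, potassium, liver enzymes, CPK, angioedema and hypotension. These are largely in any inpatient record. Losartan patients' values also come from the record under Parameters to be collected, and no losartan-specific laboratory schedule is given. This stands. It makes 50% capture of all listed AEs an extreme case, and it confines the main gap to symptoms, attribution and grading. For laboratory items the gap depends on draw frequency. The Table 1 potassium footnote expects frequent draws and suggests a repeat within 24 hours for study subjects; nothing comparable is stated for controls.

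The consent-based window can be read as covering only controls who declined losartan, since they do sign. That is a fair reading. It still leaves the historical controls, for whom the 2:1 matching is specified, with no index date. Decliners are followed by the research team, so their gap is smaller; their number is not stated.

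A reader might infer that the bias is known to run against losartan. Under-recording in controls alone would do that, but if controls are sampled more densely, laboratory capture could run the other way. The documents do not settle the net direction.

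A reader might equally infer that recording intensity could hide a large harm. For example, a true 60% against 30% is accepted 13% of the time on the percentage-point reading, but 89% if the control rate is inflated to 50%. The documents do not support assigning those 20 points to recording. Controls are matched on disease severity, and the allowance for controls with exclusion criteria is a case-mix matter, separate from how AEs are captured.

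**Conclusion.** The concern holds in a limited form. As written, the sole safety decision rule compares totals that are not collected alike. Retrospective controls have no AE window, and parts of the AE definition cannot be applied equally to them. This rests on the text, with one inference: that controls' AEs come only from the chart, because no contact is described.

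The size is illustrative. At an assumed 40% risk, control capture of 90% costs little on the percentage-point reading (0.985 to 0.973) but more on the ratio reading (0.816 to 0.647). At 75% capture the figures are 0.896 and 0.334. Capture below 83% alone pushes the expected ratio past 1.20.

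It would be too strong to say that the comparison is invalid for laboratory events, that the whole margin will be consumed, or that the direction is known. Unequal ascertainment is a familiar limit of historical controls in open-label phase 1 work, but here much of it can be removed cheaply.

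**What to change.** 1. **Comparative endpoint.** Base the safety comparison on listed AEs derivable from the record in every group: Table 1 laboratory grades, recorded hypotension and vasopressor use, angioedema, and death. Apply one extraction rule to losartan patients, decliners and retrospective controls.
2. **Index date.** Use study Day 0 (first study dose) for losartan patients. For each control, use the same number of days after first meeting entry criteria as the matched patient, with the control still in hospital and eligible then. Starting everyone at the first day criteria are met would not do: exclusion criterion 13 allows up to 48 hours before Day 0, so that would count pre-treatment events and add time that treated patients must survive to be enrolled. State how the index applies to participants who enter already on standard-of-care losartan.
3. **Window.** Use the same maximum number of days in all groups, and count only events that are new or worsened from the index date.
4. **Sampling density.** Report laboratory draws per patient-day by group. Add a sensitivity analysis using one value per day, such as the first morning value, because a common extraction rule alone does not equalise draw frequency.
5. **Other events.** Report symptom and drug-attributed AEs descriptively for the losartan group. Keep ICU transfer, ventilation and renal replacement as the separate secondary endpoints they already are.

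The cost is protocol and SAP wording plus one common extraction program; no extra patients are needed. The real downside is that symptom AEs, including the commonest losartan side effects, leave the comparative total. The use of controls with exclusion criteria is a separate case-mix question that this change does not resolve.

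### Retrospective controls for the ±20% AE/SAE rule can be chosen with their outcomes in view, because the matching is underspecified and the control list is never locked

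*Combined protocol and SAP*

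**What the plan says.** - **Design.** The Approach and Protocol section states: "This is an open label, phase 1 clinical trial to evaluate the safety of losartan in respiratory failure due to COVID-19". The number to be treated is given as "50 patients with COVID-19 and respiratory failure who meet criteria" under Clinical Trial setup.
- **Source of controls.** The Control section describes two kinds. Patients who decline losartan may agree to have their data followed. Historical controls are patients "treated at the University of Kansas Hospital in the 30 days prior to the study start date (3/25/2020) and during the study period", found by a retrospective query of the electronic record.
- **Eligibility of controls.** "These controls will be retrospectively identified through query of the electronic health record. We will attempt to include controls that meet all criteria". The criteria are those for enrolment; the second sentence then allows some controls with exclusion criteria if they are needed to reach two per participant. The only exclusion that may not be waived is prior ACE inhibitor or ARB use.
- **Matching.** Sample size and Statistics matches historical controls to participants 2:1 on age, sex and severity of disease. It names no severity measure, day of measurement, caliper, algorithm or tie-break.
- **Decision rule.** The same section accepts losartan as equivalent or superior on a ±20% "difference in total AE/SAEs". It gives no confidence interval or test. It does not say whether 20% is absolute or relative, or whether patients or events are counted.
- **Start of observation.** Definition of an Adverse Event starts AE collection at signature of the consent form. The Control section says retrospective controls give no consent, so they have no defined start day.
- **Statistical support.** Safety Reviews says: "If needed, the biostatics core will assist in data analysis for adverse events as well", on a fee-for-service basis.

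The readable text does not say who runs the query or when. It describes no masking of the selector and no locking of the control list before AEs are reviewed.

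**The concern.** The record that identifies a retrospective control can also hold the creatinine, potassium, blood pressure and vital status that make up the AE count. The trial is open label, so losartan results may also be known when controls are picked.

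The stated matching factors narrow the choice but do not determine who is chosen. Parameters to be collected lists four scores (SAPS II, NEWS, SOFA and APACHE II), and any of them could serve as severity. Without an index day, severity could be read from a point in the stay that already reflects the outcome. If eligible patients run short, the choice of ineligible fill-ins is unconstrained.

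The primary hypothesis is safety, and this comparison is its only stated criterion. If the observed difference lies near 20%, a reader could not tell afterwards whether the result reflects losartan or the choice of controls.

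**Working it through.** **Inputs.** From the documents: 50 treated patients, two controls each, margin ±20%. Not given, and therefore assumed below: the number of candidate controls and the AE rates. The plan derives no figure from an AE rate, alpha or power, so there is nothing to reproduce beyond 50 × 2 = 100 controls. I read the margin as an absolute difference in the proportion of patients with an AE, unless stated otherwise.

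**1. One swap.** Replacing one AE-free control by one with an AE moves the control proportion by 1/100 = 1 point.

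**2. A result near the margin.** Suppose 37 of 50 treated patients have an AE (74%) and 50 of 100 controls (50%).
- Absolute margin: 74 − 50 = 24 points, outside. Four swaps give 54%, and 74 − 54 = 20 points, at the margin.
- Relative margin: the control proportion must reach 74/1.2 = 61.7%, so 62 of 100, which takes 12 swaps.

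**3. Outer limits of free choice.** Let M be the number of candidates and K the number of them with an AE. Choosing 100 gives between max(0, 100 − (M − K)) and min(100, K) controls with an AE. For an outcome-blind random draw, with p = K/M, the SD in points is √[100 p(1 − p)(M − 100)/(M − 1)].

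| M | K | Pool AE rate | Outer limits | SD, blind draw |
|---|---|---|---|---|
| 100 | 50 | 50% | 50% only | 0 |
| 110 | 55 | 50% | 45–55% | 1.51 |
| 120 | 60 | 50% | 40–60% | 2.05 |
| 150 | 75 | 50% | 25–75% | 2.90 |
| 120 | 36 | 30% | 16–36% | 1.88 |
| 120 | 108 | 90% | 88–100% | 1.23 |

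For M = 120 and K = 60: minimum 100 − 60 = 40, maximum 60, SD = √(100 × 0.25 × 20/119) = √4.20 = 2.05.

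**4. When the verdict can turn.** In that example free choice moves the control proportion at most 10 points from 50%. It can change the absolute verdict on excess AEs only if the difference at the pool rate lies between 10 and 30 points. If the treated rate is also 50%, the difference runs from 50 − 60 = −10 to 50 − 40 = +10 points and never crosses 20.

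**5. Ineligible fill-ins.** If f of the 100 controls are fill-ins, the choice of which ones can move the control proportion by at most f points; for 20 fill-ins, at most 20. The direction need not be neutral. Serum potassium above 5.5 mM, low blood pressure, vasopressor need and renal insufficiency are exclusion criteria that overlap Table 1 or the stoppage criteria. Assume a 90% AE rate in fill-ins and 50% in the other controls:
- 20 fill-ins: 0.8 × 50 + 0.2 × 90 = 58%, a rise of 8 points.
- 30 fill-ins: 0.7 × 50 + 0.3 × 90 = 62%, a rise of 12 points.

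A higher control rate makes losartan look safer.

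**The case against.** Much can be said for the plan. It does specify matching on three factors, and the limits in the table ignore that constraint. Reaching those limits means leaving out only candidates with an AE, or only candidates without one, which is complete sorting on outcome. The Control section expects a shortage of eligible controls, not a surplus, and with 100 or fewer there is no choice among them. The wording about attempting to include eligible controls governs eligibility, not which eligible patient is taken. Patients who decline losartan are followed prospectively, so their outcomes are not visible at entry; if they count towards the ratio, fewer controls are picked retrospectively. Table 1 counts mild laboratory deviations as grade 1, so the AE proportion could be high and the reachable range narrow: 12 points in the last row of the table.

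These points limit the size of the problem, and they rule out three stronger readings that a reader might infer:
- **That choice of controls alone can carry any result across the margin.** Step 4 shows that it cannot when the underlying difference is far from 20 points and the pool is modest.
- **That a shift of this size would arise without intent.** No calculation supports that. The only benchmark is the outcome-blind draw, with an SD of about 2 points.
- **That the selectors will know the losartan results.** The documents do not say who selects or when, and controls also come from the study period, so some could be identified before treated results are complete.

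They do not remove the gap. Matching on an undefined severity measure, on an undefined day and by an undefined method does not fix the control list. The expected shortfall moves the discretion to the fill-ins, where no order or cap is stated.

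**Conclusion.** The concern holds as a weakness in how the comparator is built. It is not evidence that selection will be biased. The plan as written permits retrospective controls, including ineligible fill-ins, to be chosen with their AEs in view, and a margin with no interval makes a result near 20% sensitive to a few choices. With about 100 controls the sensitivity is 1 point per swap.

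The possible shift cannot be fixed from the documents. The 40% to 60% range assumes 120 candidates, a 50% AE rate and unconstrained choice; it is an outer limit that the stated matching would narrow. The range shrinks to nothing if exactly 100 candidates are available, and it widens with a larger pool. A relative or event-count reading of 20% would change the number of swaps needed. The point goes beyond missing detail because locking the list on index-day data is less open to bias than the discretionary rule, and it cannot be done convincingly once outcomes have been seen.

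**What to change.** Amend Control and Sample size and Statistics to state:

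1. **Index day.** Define one for every retrospective control, for example the first day on which all inclusion criteria are met. This is comparable to Day 0, because exclusion criterion 13 keeps Day 0 within 48 hours of that point for treated patients.
2. **Matching.** Match 2:1 on age, sex and one named severity score measured on that day, for example SOFA or NEWS. APACHE II is recorded only for ICU patients, so it cannot serve the whole group. Use a fixed algorithm with a stated caliper and a recorded seed.
3. **Shortfall.** Fill it in a pre-stated order, applied to index-day data only.
4. **Lock.** Lock and date the control list before any post-index data are extracted, with no later swaps.

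The cost is a short protocol change and a data pull in two steps, index-day data first and outcomes second. The chosen score must also be derived from the record for retrospective controls. Some fee-for-service time from the biostatistics core would be needed. Safety Reviews foresees the core only for AE analysis and only if needed, so this is a modest extension of its role.
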